# **AE** reporting to Sponsor and timelines

The Investigator must report SAEs, AESIs, and non-serious AEs which are relevant for the reported SAE or AESI, on the BI SAE form via fax immediately (within 24 hours) to the Sponsor's unique entry point (country specific contact details will be provided in the ISF). The same timeline applies if follow-up information becomes available. On specific occasions the Investigator could inform the Sponsor upfront via telephone. This does not replace the requirement to complete and fax the BI SAE form.

With receipt of any further information to these events, a follow-up SAE form has to be provided. For follow-up information the same rules and timeline apply as for initial information.

#### **Information required**

For each AE, the Investigator should provide the information requested on the appropriate eCRF pages and/or other designated data collection repository and the BI SAE form, e.g. onset, end date, intensity, treatment required, outcome, seriousness, and action taken with the

Page 63 of 144

Proprietary confidential information © 2017 Boehringer Ingelheim International GmbH or one or more of its affiliated companies

investigational drug(s). The Investigator should determine the causal relationship to the trial medication and the trial procedures outlined under Section 6.2.

The following should also be recorded as an (S)AE in the eCRF and/or other designated data collection repository and SAE form (if applicable):

- Worsening of the underlying disease or of other pre-existing conditions
- Changes in vital signs, ECG, physical examination and laboratory test results, if they are judged clinically relevant by the Investigator

If such abnormalities already pre-exist prior to trial inclusion they will be considered as baseline conditions.

All (S)AEs, including those persisting after trial completion must be followed up until they have resolved, have been sufficiently characterised, or no further information can be obtained.

# **Screening failures**

SAEs occurring in patients after having discontinued in the trial due to screening failures, i.e. after the screening period and who did not receive any trial medication, are to be reported if the Investigator considered the SAE related to the screening procedure. SAEs which occurred during the screening period are to be reported according to standard procedures.

# **Pregnancy**

In the rare case that a female patient participating in this clinical trial becomes pregnant after having taken trial medication, the Investigator must report immediately (within 24 hours) the drug exposure during pregnancy (DEDP) to the Sponsor's unique entry point (country-specific contact details will be provided in the ISF). The Pregnancy Monitoring Form for Clinical Trials (Part A) should be used.

The outcome of the pregnancy associated with the DEDP must be followed up and reported to the Sponsor's unique entry point on the Pregnancy Monitoring Form for Clinical Trials (Part B).

As pregnancy itself is not to be reported as an AE, in the absence of an accompanying SAE, only the Pregnancy Monitoring Form for Clinical Trials and not the SAE form is to be completed. If there is an SAE associated with the pregnancy then the SAE has to be reported on the SAE form in addition.

The ISF will contain the Pregnancy Monitoring Form for Clinical Trials (Part A and B).

c03024901-03 Trial Protocol Version 3.0

Page 64 of 144

04 Jan 2017

c03024901-03 Trial Protocol Version 3.0

Page 65 of 144

04 Jan 2017

c03024901-03 Trial Protocol Version 3.0

04 Jan 2017

Page 66 of 144

c03024901-03 Trial Protocol Version 3.0

04 Jan 2017

Page 67 of 144

#### 5.7 APPROPRIATENESS OF MEASUREMENTS

All measurements performed during this trial are considered standard measurements in the clinical development of a non-insulin product such as empagliflozin, and/or standard as part of routine care for T1DM [R08-2669, R14-0344]. All defined measurements will be performed in order to monitor safety and tolerability aspects and to determine efficacy and PK in an appropriate way.

A surrogate endpoint (i.e. the laboratory parameter  $HbA_{1c}$ ) is used as the primary efficacy endpoint, since for the purposes of drug approval and labeling, which will support an indication of glycaemic control, regulatory authorities state that this endpoint, albeit surrogate, is the primary endpoint of choice [R08-2669].

Electronic devices have been selected as the method for PROs. Use of a PRO instrument is advised when measuring a concept best known by the patient or best measured from the patient perspective (e.g. symptoms associated with hypoglycaemia). PRO instruments should be shown to measure the concept they are intended to measure, and steps should be taken to ensure that patients are making entries according to the design of the trial and not, for example, just before a clinic visit [R12-5607]. Hence the selection of an electronic device over a paper-based alternative.

Page 69 of 144

Proprietary confidential information © 2017 Boehringer Ingelheim International GmbH or one or more of its affiliated companies

# 6. INVESTIGATIONAL PLAN

#### 6.1 VISIT SCHEDULE

All trial visits should take place in the morning (e.g. between 7am and 11am). All patients must adhere to the visit schedule as specified in the Flow Chart. If permitted visit windows are applied to a visit involving CGM, it must be ensured that the CGM sensor is still exchanged within its period of stability (i.e. 7 days since insertion), despite the use of the window.

If any visit has to be re-scheduled, subsequent visits should follow the original visit schedule. The trial medication kits will contain sufficient medication to allow for the protocol-permitted visit windows.

If a patient mistakenly takes trial medication on the morning of a visit before attending the clinic (excluding visits prior to randomisation) or comes in non-fasted where a fasting condition is required, the visit should be re-scheduled to the next day reminding the patient about the expected conditions. At the relevant visits, it must also be ensured that the CGM sensor is still exchanged within its period of stability (i.e. 7 days since insertion) despite the re-scheduling of a visit.

# 6.2 DETAILS OF TRIAL PROCEDURES AT SELECTED VISITS

At each visit, assessments should be performed as indicated in the Flow Chart and as detailed in the respective protocol sections.

# 6.2.1 Screening, T1DM therapy optimisation and placebo run-in periods

# 6.2.1.1 Screening visit (Visit 1)

- The screening visit does not need to be done with the patient in a fasted state (see Section 5.3.3)
- No trial procedures should be done unless the patient has consented to taking part in the trial. Once they have consented, the patient is considered to be enrolled in the trial and to have started screening. The patient should be recorded on the enrolment log and be registered in the IRT system as a screened patient
- BP should always be measured before any blood samples are taken. For details regarding the correct method for measuring BP, see Section 5.2.4
- Patients who are not eligible to proceed to Visit 2 should be registered as a screen failure in the IRT system and the eCRF and no further follow-up is required

# 6.2.1.2 T1DM therapy optimisation period (Visits 2, 3/3T and 4T)

• Visit 2 should be done with the patient in a fasted state (i.e. no food or drink except water for 10 hours) (see Section 5.3.3)

•

- Visit 3T, if performed as a telephone visit, does not require attendance at the clinic. If performed as a clinic visit, Visit 3 does not need to be done with the patient in a fasted state (see Section 5.3.3)
- Visit 4T is a telephone visit and does not require attendance at the clinic
- Each visit should only be performed once it has been confirmed that the patient is eligible to progress to the next visit; ineligible patients should be registered in the IRT system and the eCRF as a screen failure and no further follow-up is required
- BP should always be measured before any blood samples are taken (relevant for Visit 2 only). For details regarding the correct method for measuring BP, see Section 5.2.4
- At the end of each visit, patients should be reminded about the importance of entering data into their e-diary on a daily basis, including data from the glucose/ketone meter, so that optimisation of the T1DM therapy can be monitored remotely by designated site-personnel, and an assessment made of the need for weekly telephone discussions and/or additional visits

# 6.2.1.3 Placebo run-in period (Visit 5)

- Visit 5 does not need to be done with the patient in a fasted state (see Section 5.3.3)
- Visit 5 should only be performed once it has been confirmed that the patient is eligible to progress to this visit, based on an assessment of results from Visits 2 to 4T
- As for Visit 1, BP should always be measured before any blood samples are taken. For details regarding the correct method for measuring BP, see Section 5.2.4
- Following completion of the Visit 5 procedures, eligible patients will be dispensed a placebo run-in kit for the 2 week run-in period which will be assigned via the IRT system. Ineligible patients should be registered in the IRT system and the eCRF as a screen failure and no further follow-up is required
- From Visit 5, eligible patients will also start the first CGM period (in participating countries) and will continue this until Visit 6. If the patient wishes to perform the first 2 hour start up calibration of the CGM system (using his/her glucose meter) whilst at the site, this should be taken into consideration when planning the order of assessments at this visit (for further details, refer to CGM system user guide). If deemed necessary by the site personnel, patients can be contacted by phone in between these visits to ensure the correct performance of the CGM device. Patients must also be reminded to change the CGM sensor at home, 7 days after its insertion at Visit 5

•

# 6.2.2 Randomised treatment period

The randomised treatment period is from Visit 6 to Visit 16 EOT.

Throughout the treatment period, BP should always be measured before any blood samples are taken. For details regarding the correct method for measuring BP, see Section 5.2.4.

Laboratory samples should also be taken prior to the intake of trial medication at clinic visits throughout the treatment period.

All patients, including those who discontinue treatment early, must be followed up until the end of the study. Patients must continue to be followed up according to the visit schedule (unless they withdraw consent for further follow-up) in order to collect data at the end of the planned observation period. For further details see Section 6.2.3.

# 6.2.2.1 Randomisation visit (Visit 6)

• Visit 6 should be done with the patient in a fasted state (i.e. no food or drink except water for 10 hours), and only once it has been confirmed that the patient is eligible to progress to randomisation. This includes a check of the data from the patient e-diary, and

•

- Eligible patients will be randomised on Day 1 by using the IRT system; all visit assessments should have been completed prior to this, and before the first intake of study medication
- At Visit 6 (Day 1) the patient should also be reminded to contact the site without delay if he/she has any questions or concerns with respect to insulin adjustments. The patient should also be reminded to increase the frequency of SBGM testing for 5 days from the day of randomisation (i.e. on Days 1-5),

Where considered necessary, the patient should be called daily for 5 days following Day 1 to discuss further adjustment of their insulin therapy; additional clinic visits should be scheduled if closer monitoring of the patient is warranted

# 6.2.2.2 Interim visits (Visits 7-15)

• Visits 9, 12 and 14 should be done with the patient in a fasted state (i.e. no food or drink except water for 10 hours); Visits 7, 8, 10, 11, 13 and 15 do not require fasting

•

• Prior to each clinic visit, patients should be reminded to attend without having taken their trial medication in the morning, and to bring all used/unused medication with them to the visit

•

• At Visit 11, the second CGM period starts (for participating countries), and continues for 28 days until Visit 12. If deemed necessary by the site personnel, patients can be contacted by phone in between visits to ensure the correct performance of the CGM device. Patients must also be reminded to change the CGM sensor at home, every 7 days

Page 72 of 144

Proprietary confidential information © 2017 Boehringer Ingelheim International GmbH or one or more of its affiliated companies

after its insertion at Visit 11. For countries not participating in the CGM assessment, Visit 11 is not required

• At Visit 15, the third CGM period starts (for participating countries), and continues for 28 days until Visit 16 at which point the transmitter and sensor will be removed from the patient. If deemed necessary by the site personnel, patients can be contacted by phone in between visits to ensure the correct performance of the CGM device. Patients must also be reminded to change the CGM sensor at home, every 7 days after its insertion at Visit 15. For countries not participating in the CGM assessment, Visit 15 is not required

•

# 6.2.3 End of treatment and follow-up period

# 6.2.3.1 End of treatment – completers (Visit 16 EOT)

Patients who successfully complete the 52 week treatment period should have the assessments for Visit 16 performed, as indicated in the Flow Chart. Patients who complete the full 52 week treatment period should be registered as completed in the IRT system.

• Visit 16 EOT should be done with the patient in a fasted state (i.e. no food or drink except water for 10 hours), and patients should be reminded to attend without having taken their trial medication in the morning as they will take the last dose at the site, and to bring all used/unused medication with them to the visit. The patient should be reminded not to start any new anti-diabetic therapy until after Visit 17

•

• Patients should be reminded to continue with e-diary entries, checks of glucose and ketones using the glucose and ketone monitoring device for another 3 weeks until Visit 17

# 6.2.3.2 End of treatment - early discontinuations (eEOT) and withdrawals

Patients who discontinue study medication early should have the assessments for eEOT (Early Discontinuations Only) performed, as indicated in the Flow Chart. For such patients, the eEOT Visit should be done as soon as possible after the decision to discontinue has been made. If the eEOT Visit occurs within the time window of a scheduled visit and the patient continues to be followed up, the eEOT Visit will replace that scheduled visit. For example:

• if a patient discontinues study medication 16 weeks after randomisation (i.e. between Visits 9 and 10), the eEOT Visit could be scheduled one week later, and it would occur within the time window of the next scheduled visit (i.e. Visit 10 at Week 18 ± 7 days). When returning to the visit schedule, after completing the 3 week Follow-up Visit (see Section 6.2.3.3 below), the patient would return for Visit 11 at Week 22

If a patient intends to immediately discontinue (withdraw) from the study, an eEOT Visit should be performed as soon as possible after the decision to withdraw has been made.

Page 73 of 144

Proprietary confidential information © 2017 Boehringer Ingelheim International GmbH or one or more of its affiliated companies

Patients who discontinue treatment prematurely (prior to 52 weeks) but continue to be followed up should be registered as "withdrawn from treatment" in the IRT system, whereas patients who withdraw from the trial should be registered as "withdrawn from study".

• eEOT should be done with the patient in a fasted state (i.e. no food or drink except water for 10 hours), and patients should be reminded to bring all used/unused medication with them to the visit. The patient should be reminded not to start any new anti-diabetic therapy until after Visit 17

•

- Patients should be reminded to continue with e-diary entries, checks of glucose and ketones using the glucose and ketone monitoring device for the remainder of the observation period
- 6.2.3.3 Follow-up visit (Visit 17) completers

Patients who successfully complete the 52 week treatment period should have the assessments for Visit 17 performed, as indicated in the Flow Chart. For these patients:

- Visit 17 should be done with the patient in a fasted state (i.e. no food or drink except water for 10 hours)
- The patient e-diary will be checked after which it should be removed from the patient, together with all other study-related devices and equipment, once Visit 17 is complete
- 6.2.3.4 Follow-up visit (Visit 17) early discontinuations (eEOT) and withdrawals

For patients who discontinue treatment prematurely prior to completion of 52 weeks the following should be performed whenever possible once an eEOT Visit has been completed (see Section 6.2.3.2):

- 3 weeks after the date of the eEOT Visit, patients should complete Visit 17. Visit 17 should be done with the patient in a fasted state (i.e. no food or drink except water for 10 hours), and all assessments indicated in the Flow Chart for Visit 17 should be performed
- Thereafter, patients should be followed up according to the visit schedule (e.g. a patient who discontinued study medication a week after Visit 12 (Week 26) i.e. at Week 27 would next be followed up for Visit 13 (Week 34) after having completed an eEOT visit as soon as possible after Week 27, and a Visit 17 at Week 30
- The Investigator may negotiate a revised visit schedule should the patient be unwilling or unable to adhere to the regular schedule according to the Flow Chart. These follow-up visits may occur by telephone or in the clinic but Visit 12 (Week 26) and Visit 16 (Week 52) must be performed as a clinic visit in order to complete all scheduled assessments
- When being followed up according to the visit schedule, only assessments relating to the primary and key secondary endpoints and general safety have to be completed (i.e. weight, vital signs, physical examination, ECG, safety laboratory, pregnancy test, HbA1c, e-diary completion, CGM periods (in patients from participating countries) and the

Page 74 of 144

Proprietary confidential information © 2017 Boehringer Ingelheim International GmbH or one or more of its affiliated companies

collection of AEs and changes in concomitant therapy). All other assessments

• Visit 16 EOT at 52 weeks will be the last visit for these patients, since Visit 17 will already have been completed 3 weeks after the eEOT Visit as explained above. At Visit 16 EOT therefore, the patient e-diary will be checked after which it should be removed from the patient, together with all other study-related devices and equipment, once the visit is complete

For patients who discontinue treatment prematurely and do not wish to follow the visit schedule, at least a contact should be planned, at the timepoint of the primary endpoint at 26 weeks, and at the main analysis after 52 weeks, to collect data about the vital status as a minimum.

If study treatment is stopped prior to completion of 52 weeks and the patient intends to immediately discontinue (withdraw) from the study, an eEOT Visit should be performed as soon as possible after the decision to withdraw has been made. The patient should return for a Visit 17 (3 weeks after the eEOT). At this visit all assessments should be performed according to the Flow Chart.

Page 75 of 144

Proprietary confidential information © 2017 Boehringer Ingelheim International GmbH or one or more of its affiliated companies

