- An early End of Treatment (eEOT) Visit, as well as a Follow-up Visit 17, should be performed for any patient who discontinues study medication prematurely; the eEOT Visit should be completed as soon as possible after study medication is stopped. PK sampling can be omitted if the eEOT Visit is not performed within 24 hours of the last dose of study medication; the 8-point plasma glucose profile should only be performed if it is feasible for it to be done over a 24 hour period before the eEOT Visit when study medication is still being taken; otherwise it can be omitted. Visit 17 should be performed 3 weeks after the eEOT visit, and where possible, patients should then be followed up according to the visit schedule. For further details see Section 6.2.3
- H NF: non-fasting; F: fasting

Ε

- J Following the termination of trial medication, and if deemed necessary based on Investigator's judgement, additional support (e.g. telephone interaction) can be given to the patient during the adjustment of T1DM therapy in the Follow-up period
- K Safety laboratory includes calculation of the eGFR. Following a positive urine dipstick result (at the site) for leukocyte esterase (for WBC) or nitrite, a midstream urine sample for urine culture is triggered. For further details see Section 5.3.3
- L For female patients of child-bearing potential (local urine pregnancy test) M

O Home monitoring device: meter for monitoring of blood (plasma) glucose and ketone levels at home

- Self-Blood Glucose Monitoring (SBGM) should be performed daily from the beginning of the T1DM therapy optimisation period to the end of the Follow-up period. Measurements should be taken 4 times a day as a minimum e.g. at least before breakfast, lunch, dinner and bedtime. Additional measurements will also be warranted (e.g. after clinic Visit 6). For further details see Section 5.3.2.1. Ketone measurements should be performed by the patient in case of any symptoms of DKA. Other conditions may also trigger the need for ketone measurement. For further details see Footnote AA and Section 5.3.2.2

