# 5.3.7 Adverse event collection and reporting

#### **AE** collection

The following must be collected and documented on the appropriate eCRF and/or other designated data collection repository by the Investigator (see also Figure 5.3.7: 1 below):

• From signing the informed consent onwards through the Residual Effect period (REP), until trial completion, all AEs (serious and non-serious), and AESIs

• If in an individual patient only vital status information is collected from a certain time point on, no further AEs or AESIs will be reported for this patient

[figure not shown]

Figure 5.3.7: 1 Trial periods for collection of AEs

The REP is defined as 7 days after the last trial medication application, except for hypoglycaemia, where the REP is 1 day. All AEs which occurred through the treatment period and throughout the REP will be considered as on treatment (please see Section 7.3.4). Events which occurred after the REP will be considered as post-treatment events.

After the last per protocol contact the Investigator does not need to actively monitor patients for AEs. However, if the Investigator becomes aware of SAEs or AESIs that occurred after the last per protocol contact, the SAEs and AESIs should be reported by the Investigator to the Sponsor if considered relevant by the Investigator.

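### For patients who stop treatment late but stay in follow-up, Protocol 6.2.3.4 closes them out at Visit 16 on the false ground that Visit 17 is already done

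*Protocol*

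**What the plan says.** Protocol 6.2.3.4 covers everyone who stops treatment before completing 52 weeks, with no upper limit on when they stop. Its first bullet sets the off-drug visit: "3 weeks after the date of the eEOT Visit, patients should complete Visit 17". The Flow Chart footnote on early discontinuation agrees: "Visit 17 should be performed 3 weeks after the eEOT visit".

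The last bullet, for those who stay in follow-up, reads "Visit 16 EOT at 52 weeks will be the last visit for these patients, since Visit 17 will already have been completed 3 weeks after", counting from the eEOT visit. It then draws the consequence: "At Visit 16 EOT therefore, the patient e-diary will be checked after which it should be removed from the patient", along with the other study devices.

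Four other places bear on the point:

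- Protocol 5.2.3 and 5.3.2.1 provide the e-diary and the self-monitoring equipment to all patients until Visit 17.
- Protocol 6.2.3.1 has completers keep up diary entries and "checks of glucose and ketones using the glucose and ketone monitoring device for another 3 weeks until Visit 17".
- Protocol 6.2.3.2 says that when an eEOT falls inside the window of a scheduled visit, "the eEOT Visit will replace that scheduled visit".
- The closing paragraph of 6.2.3.4 gives patients who leave the study altogether a separate rule: they return for Visit 17 three weeks after the eEOT. That rule has no fault.

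**The concern.** The last bullet states as fact that Visit 17 precedes Visit 16, and builds an instruction on it. The statement is true for the section's only worked example, a patient who stops at Week 27. It cannot be true for a patient whose eEOT is less than three weeks before Visit 16. For that patient the first bullet still requires Visit 17, while the last bullet ends participation and takes back the equipment beforehand.

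At stake is off-drug monitoring. Protocol 4.2.1 asks for special caution over hypoglycaemia, hyperglycaemia and ketoacidosis in the Follow-up period, when empagliflozin is stopped. Protocol 3.2 justifies the three weeks partly as a check on reversibility of side effects. A completer has 21 days of diary, glucose and ketone checks after the last dose. A patient whose last dose and eEOT are on Day 361 would have 4 days if the site followed the bullet.

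**Working it through.** **Inputs**

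- Visit 16: planned Day 365, window +/- 3 days, so Days 362-368 (Flow Chart).
- Visit 17: eEOT + 21 days (6.2.3.4 and the Flow Chart footnote). The Flow Chart gives Visit 17 a window of +/- 7 days. I assume it also applies to a Visit 17 timed from the eEOT, giving eEOT + 14 to eEOT + 28.

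**Reproducing the plan's own dates**

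Study day = 7 x week + 1. Week 52 gives 7 x 52 + 1 = 365, and 365 + 21 = 386; both match the Flow Chart. The example in 6.2.3.4, a stop at Week 27, gives 27 + 3 = Week 30, as stated.

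**When does Visit 17 come no later than Visit 16?**

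- Planned schedule: eEOT + 21 <= 365, so eEOT <= Day 344.
- Most favourable windows: eEOT + 14 <= 368, so eEOT <= Day 354.

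| eEOT day | Visit 17 planned | Visit 17 earliest | Visit 17 no later than Visit 16? |
|---|---|---|---|
| 344 | 365 | 358 | yes, as planned |
| 345 | 366 | 359 | only by using the windows |
| 354 | 375 | 368 | only with Visit 16 at its latest, Day 368 |
| 355 | 376 | 369 | no |
| 361 | 382 | 375 | no |
| 362-364 | 383-385 | 376-378 | not applicable: the eEOT replaces Visit 16 |

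**How many patients?**

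The documents give no discontinuation rate. Assume that 10-20% of 720 patients (72-144) stop early, evenly over Days 1-364, all stay in follow-up, and have the eEOT on the stop day.

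- Unavoidable conflict, Days 355-361: 7/364 = 1.9%; x 72 = 1.4, x 144 = 2.8.
- Conflict on the planned schedule, Days 345-361: 17/364 = 4.7%; x 72 = 3.4, x 144 = 6.7.

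**What does each patient lose if the site acts on the bullet?**

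Days between Visit 16 and Visit 17 on the planned schedule = eEOT + 21 - 365. This is 1 day for an eEOT on Day 345, 11 for Day 355 and 17 for Day 361. Off-drug days before the equipment is taken back = 365 - eEOT: 20, 10 and 4 days respectively.

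**The case against.** The best defence is that the bullet carries its own condition. It gives its reason, and ties the return of equipment to that reason. The bullets also run in sequence (Visit 17, then back to the schedule, then Visit 16 last), so *these patients* can be read as those who resumed the schedule after Visit 17. The rest of the protocol points the same way: 5.2.3 and 5.3.2.1 keep the diary and meter until Visit 17, 6.2.3.2 continues the checks for the rest of the observation period, and 3.1 ends participation at Visit 17. Attendance under 6.2.3.4 is also qualified by what is possible, and the schedule may be negotiated.

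Much of this stands. It shows what was intended, and a site following the first bullet loses nothing. But the bullet is worded without a time limit, and reading one into it requires the site to notice that the stated reason is untrue. This assessment rests on the visible text, since the sentence just before the bullet is cut off.

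A reader might infer more than the documents support:

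- *That every eEOT after Day 344 is in unavoidable conflict.* The windows allow the right order up to Day 354.
- *That an eEOT on Days 362-364 is a second conflict.* There the eEOT replaces Visit 16, so there is no separate Visit 16 at which to take the equipment back. The first bullet alone governs, and Visit 17 is the last visit.
- *That Visit 17 is waived, or that nothing else in the protocol speaks to the case.* No text waives it, and the sections above indicate the answer.
- *That adverse-event collection stops early or the 7-day residual effect period is cut short.* Protocol 5.3.7 does say "After the last per protocol contact the Investigator does not need to actively monitor patients for AEs", but a Visit 17 still due is itself such a contact. The same section also requires collection through the residual effect period until trial completion. Losing those data would need a breach of 5.3.7 as well as a literal reading of the bullet.

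**Conclusion.** The inconsistency is real, narrow and minor. For patients who remain in follow-up with an eEOT on Days 355-361, no permitted scheduling makes the last bullet of 6.2.3.4 true. It conflicts with the first bullet, the Flow Chart footnote, 5.2.3 and 5.3.2.1. For Days 345-354 the conflict exists on the planned schedule but can be scheduled away.

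The counts of about 1-3 and 3-7 patients rest on the assumed 10-20% discontinuation, even timing, full retention and same-day eEOT; none of these comes from the documents. The day limits refer to the eEOT, so if the eEOT lags the last dose, the matching stop day is earlier. The loss occurs only where a site acts on the bullet, and it is confined to post-treatment diary, glucose and ketone follow-up and the risk of missing Visit 17. The Week 26 primary and key secondary analyses are unaffected.

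**What to change.** Replace the last bullet's rule with: for patients who remain in follow-up, the last visit and the return of the e-diary and devices occur at Visit 16 or at Visit 17 (eEOT + 3 weeks), whichever is later.

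This costs one clause and a reminder to sites. It adds no visit, because Visit 17 is already required, and needs no change to the SAP. The downside is that a few devices come back later: up to 17 days on the planned schedule, or 17 + 7 = 24 days if Visit 17 falls at the end of its window.
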